9.14 Dose Escalation Stopping Rules

Dose escalation can be stopped if any treatment-emergent adverse event (TEAE) occurs in a subject dosed with NAL ER during the study that, in the opinion of the Investigator, raises concerns about the safety and tolerability of a higher dose. In addition, the following dose escalation rules will apply.

Dose-limiting toxicity (DLT) in the hepatic-impaired subject population participating in this study is defined as the dose at which a confirmed Grade 3 adverse event develops in any 2 subjects, even if in two different organ systems, that is IP related and is unlikely to be related to the disease process. Overnight oximetry that drops more than 10% from a subject's baseline lowest value for a consistent period of 5 minutes will be considered a DLT TEAE.

Any subject who experiences a DLT TEAE will not receive further dose of study drug, and safety follow-up procedures will be performed.

9.14.1 Part 1 (SAD) Dose Escalation Procedures and Stopping Criteria for Subjects with Mild and Moderate Hepatic Impairment (Group 1 and Group 2)

Upon completion of the dosing of subjects with mild and moderate hepatic impairment (Group 1 and Group 2) in each of Cohorts 1 to 4 in Part 1 of the study, the safety data and nalbuphine PK parameters (if available or requested) will be reviewed by the Safety Committee to determine the continuation of the progression of Part 1 dose escalation and to evaluate the safety for that dose level to be included in Part 2 of the study (MAD).

If 2 subjects develop a DLT at the same dose, then that dose will be confirmed as DLT.

If 2 subjects develop a DLT at 2 different doses (eg, 108 mg and 162 mg), then the higher of the 2 doses (162 mg in this example) will not be pursued in remaining Group 1 and Group 2 subjects (if not already dosed).

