	
 
 5 (healthy subjects)	Up to 162 mg	
 
 
For Cohort 1, a minimum of 6 subjects from Group 1 (mild impairment), 6 subjects from Group 2 (moderate impairment), and 4 subjects from Group 3 (severe impairment) will receive a single dose of NAL ER.
 
For Cohorts 2-4, a minimum of 6 subjects from Group 1 (mild impairment) and 6 subjects from Group 2 (moderate impairment) will receive a single dose of NAL ER. Cohort 5 (healthy) will also receive a single dose of NAL ER as determined by the Safety Committee review of the mild and moderate impaired data.
 
Cohorts 1-4 will be dosed sequentially in an ascending design. Enrollment of subjects with mild impairment and moderate impairment can be done in parallel. Subjects with severe impairment will be enrolled upon completion of the highest dose level in mild and moderate impairment subjects. There will be at least 7 days between dosing of each dose level, within the same group of impairment (mild and moderate). Subjects will be observed for a period of 4 days.
 
Safety, tolerability, and combined mild and moderate impaired subject data will be evaluated by a Safety Committee at the completion of each cohort dose level before proceeding to the next cohort dose level. Therefore, the highest dose administered may be lower than 162 mg. Depending on safety and tolerability, the dose escalation scheme may be modified such that intermediate dose levels are administered.
 
Based on the overall safety and tolerability observed in the subjects with mild and moderate impairment, at the completion of all doses tested, it will be determined by the Safety Committee whether or not it is safe to proceed with dosing for the first 2 subjects with severe impairment starting with the 27 mg dose. After review of the safety and tolerability for the first 2 severe subjects dosed, it will be determined whether or not to complete that dose level for the remaining 2 severe subjects at the 27 mg dose.
 
The Safety Committee will be composed of at least the Investigators and one medically qualified Sponsor representative. Some adjustments to the currently outlined doses and/or dosing regimen may be implemented by the Safety Committee, but the dose to be administered in a given dose cohort will not exceed the one currently outlined in the protocol.
 
No food will be allowed from at least 8 hours before NAL ER dosing until at least 2 hours after. A standardized breakfast will be served at least 2 hours after NAL ER dosing. A lunch, supper, and a light snack will be served at appropriate times thereafter. Except for water given with NAL ER, no fluids will be allowed from 1 hour before dosing until 1 hour post-NAL ER dose.
 
Part 2 (MAD)
 
Drug administration in Part 2 of the study (MAD) may be initiated following satisfactory review of the safety and tolerability data from Groups 1 and 2 (mild and moderate impairment) from Part 1 of the study (SAD) by the Safety Committee. Depending on safety and tolerability, the dose escalation scheme may be modified such that intermediate dose levels are administered. The dosage regimen (once daily versus twice daily) will be confirmed following review of PK data, as available, from Part 1 of the study (SAD). Part 1 subjects may enter Part 2 of the study after a 7 day washout period.
 
Subjects will receive a single 27 mg dose in the morning of Day 1. Doses will be subsequently escalated for each subject to twice daily, 12 hours apart, 27 mg, 54 mg, 108 mg, and 162 mg over 13 days. On the last treatment day,
	5 (healthy subjects)	Up to 162 mg

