- 2) Clinically significant abnormalities of laboratory, ECG, pulse oximetry, or clinical data that would preclude participation in the study in the opinion of the Investigator. Clinical data, ECG, and laboratory results may be repeated at the discretion of the Investigator.
- 3) Presence of hepatocellular carcinoma or acute hepatic disease from infection or drug toxicity.
- 4) Presence of stage 3 or stage 4 encephalopathy.
- 5) History of any illness that, in the opinion of the Investigator might confound the results of the study or pose an additional risk to the subject by participation in the study. Subjects who do not qualify based on a reversible medical condition or mild inter-current illness may be re-evaluated after further testing/examination or re-screened after the condition is resolved.
- 6) Presence of surgically-created or transjugular intrahepatic portal systemic shunts.
- 7) Clinically significant illness or surgery within 4 weeks prior to dosing.
- 8) Positive test for HIV.
- 9) Estimated glomerular filtration rate (eGFR) by the MDRD4 Equation $< 50 \text{ mL/min/1.73 m}^2$ at screening.
- 10) Clinically significant history or presence of any gastrointestinal pathology that will interfere with IP absorption (eg, malabsorption syndrome, chronic diarrhea, inflammatory bowel diseases).
- 11) Positive urine drug screen at screening or Baseline (Day -1) unless the positive drug screen is due to prescription drug use that is approved by the Investigator.
- 12) History of allergic reactions to nalbuphine, opioids, or other related drugs.
- 13) Subject has a history of anaphylaxis, a documented hypersensitivity reaction, or a clinically significant reaction to any drug.
- 14) Use of any drugs known to be strong inducers or strong inhibitors of hepatic drug metabolism within 30 days prior to the IP administration.
- 15) Use of any mu-opioid agonist or mu-antagonist such as naltrexone within 14 days of screening.
- 16) Positive pregnancy test at screening or on Day -1 (females only).
- 17) Any reason which, in the opinion of the Investigator, would prevent the subject from participating in the study.
- 18) History of ventricular tachycardia, torsade de pointes, family history of sudden death, myocardial infarction or acute coronary syndrome within the previous 3 months, as reported by the subject.

- 19) Clinically significant findings on ECG as determined by the Investigator at screening, or:

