9.1 Screening Procedures

Subject screening procedures will be performed within 28 days preceding administration of the IP. Subjects must provide written informed consent prior to initiation of any screening procedures. The study-specific ICF must be signed and dated by the subject before participation to study-specific procedures.

Screening procedures will include: demographic data, medical and medication histories, complete physical examination, body measurements, ECG, vital signs, pulse oximetry, body temperature, hematology, coagulation, clinical chemistry, HIV, HBsAG and HCV, urinalysis, WI-NRS for itching (Part 2 only), urine and serum pregnancy test, and urine alcohol and drug screen.

Assessment of liver function will be performed and the degree of hepatic impairment will be categorized using Child-Pugh system at screening.

Subjects from Cohorts 1 to 4 (mild and moderate groups) will be recruited prior to recruiting healthy control group subjects (Cohort 5) in order to facilitate subjects' matching.

For eligibility purposes, abnormal laboratory or vital signs results may be repeated if abnormal result is observed at the initial reading. Moreover, abnormalities found in the ECG may need to be confirmed by repeated measurements. In the event that the participation of a subject in the study is delayed and some screening procedures had been performed outside the prescribed screening window, outdated screening procedures can be repeated. For inclusion, Child-Pugh categorization laboratories that are deemed inconsistent with the usual stage of hepatic impairment may be repeated.

Subjects who do not qualify based on a reversible condition or mild intercurrent illness may be re-screened after the condition is resolved.

Qualified subjects may participate in multiple cohorts (if they remain eligible) and screening procedures do not need to be repeated between cohorts. It is the responsibility of the Investigator to review and confirm that subjects continue to meet all inclusion and exclusion criteria prior to advancing subjects to the next cohort.

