9.4 Investigational Product (IP)

The Investigational Product (IP) NAL ER tablets (4 strengths) will be supplied by the Sponsor. NAL ER tablets, 27 mg and 54 mg, are white to off-white film coated round tablets (7.9 mm). The NAL ER tablets 108 mg (7.6×15.7 mm) and 162 mg (9.3×15.4 mm) are white to off-white film coated oblong tablet. NAL ER tablets will be shipped to the Pharmacy packaged in 70 count HDPE bottles with an induction inner seal and child-resistant (CR) closures.

In Part 1 of the study (SAD), hepatic impaired subjects will receive single ascending oral doses and healthy subjects will receive a single oral dose, under fasting conditions, of NAL ER, at the following dose levels:

Cohort	Planned Dose of NAL ER
1	27 mg
2	54 mg
3	108 mg
4	162 mg
5 (healthy subjects)	Up to 162 mg

For Cohort 1, a minimum of 6 subjects from Group 1 (mild impairment), 6 subjects from Group 2 (moderate impairment), and 4 subjects from Group 3 (severe impairment) will receive a single dose of NAL ER.

For Cohorts 2-5, a minimum of 6 subjects from Group 1 (mild impairment) and 6 subjects from Group 2 (moderate impairment) will receive a single dose of NAL ER.

Cohorts will be dosed sequentially in an ascending design. Enrollment of subjects with mild impairment and moderate impairment can be done in parallel. Subjects with severe impairment will be enrolled upon completion of the highest dose level in mild and moderate impairment subjects. There will be at least 7 days between dosing of each dose level, within the same group of impairment (mild and moderate). Subjects will be observed for a period of 4 days.

Safety, tolerability, and combined mild and moderate impaired subject data will be evaluated by a Safety Committee at the completion of each cohort dose level before proceeding to the next cohort dose level. Therefore, the highest dose administered may be lower than 162 mg. Depending on safety and tolerability, the dose escalation scheme may be modified such that intermediate dose levels are administered.

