Based on the overall safety and tolerability observed in the subjects with mild and moderate impairment, at the completion of all doses tested, it will be determined by the Safety Committee whether or not it is safe to proceed with dosing for the first 2 subjects with severe Impairment. After review of the safety and tolerability for the first 2 severe subjects dosed at 27 mg, it will be determined whether or not to complete that dose level for the remaining severe subjects.

At the completion of all subjects dosed in the cohort, there will be an evaluation of safety and tolerability to determine whether to proceed to the next dose level for this group.

The Safety Committee will be composed of at least the Investigators and one medically qualified Sponsor representative. Some adjustments to the currently outlined doses and/or dosing regimen may be implemented by the Safety Committee, but the dose to be administered in a given dose cohort will not exceed the one currently outlined in the protocol.

Drug administration in Part 2 of the study (MAD) may be initiated following satisfactory review of the safety and tolerability data from Groups 1 and 2 (mild and moderate impairment) from Part 1 of the study (SAD) by the Safety Committee. Depending on safety and tolerability as well as on available PK data, the dose escalation scheme may be modified such that intermediate dose levels are administered. The dosage regimen (once daily versus twice daily) will be confirmed following review of PK data from Part 1 of the study (SAD).

If in the judgement of the Safety Committee the Part 1 PK data demonstrates dose linearity across the dose range in both the mild and moderate hepatic impairment subjects (Group 1 and Group 2 subjects), such that PK modeling can be predictive of steady state dosing levels, a decision may be made to end the study without conducting Part 2 of the study

In Part 2 of the study (MAD), subjects will receive a single 27 mg dose in the morning of Day 1. Starting on Day 2, doses will be subsequently escalated for each subject to twice daily, 12 hours apart, 27 mg, 54 mg, 108 mg, and 162 mg over 13 days. On the last treatment day, (Day 13), subjects will receive a single 162 mg dose in the morning. Subjects will remain at each dose level for 2-3 days (minimum 5 consecutive doses) with dose escalation predicated on tolerability of the prior dose (See Section [9.14.4](#) for dose escalation stopping rules).

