9.11 Discharge/Study Exit Procedures

For Part 1 of the study, the following will be performed on Day 4: brief physical examination, vital signs, body temperature, ECG, pulse oximetry, clinical chemistry, hematology, coagulation, urinalysis, PK sample, urine and serum pregnancy test (females only), and adverse events monitoring.

For Part 2 of the study, the following will be performed on Day 16: brief physical examination, vital signs, body temperature, ECG, pulse oximetry, clinical chemistry, hematology, coagulation, urinalysis, PK sample, urine and serum pregnancy test (females only), WI-NRS, and adverse events monitoring. The following will be performed on Day 17: PK sample.

If not possible, all efforts will be made to complete study exit procedures within 14 days after the last participation of the subject in the study.

In the case that a subject experiences a DLT or a DLT dose is confirmed in 2 subjects during Part 2 (MAD), post last-dose study procedures will be performed as laid out in the DLT Follow-Up Period (see Section [9.11.1](#)). Early Termination procedures are only applicable to subjects who discontinue study drug for reasons other than those related to DLT.

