9.11.1 DLT Follow-Up Period for Part 2 (MAD), Post-Last Dose

In Part 2 of the study, any subject who experiences a DLT TEAE will not receive further dose of study drug, and safety follow-up procedures, per the DLT Follow-Up Period will be performed.

If 2 subjects develop a DLT, all subjects who are currently receiving a confirmed DLT dose will not receive further dose of study drug and will immediately enter into the DLT Follow-Up Period.

The maximum safe dose (MSD) will be determined as the dose level below the DLT dose.

Subsequent subjects in Part 2 of the study will only be dosed through the completion of the MSD per the days specified in the titration table. After dosing is complete, subjects will immediately enter the DLT Follow-Up Period and the following procedures will be performed:

DLT Follow-Up Period Procedures

- Subjects will be confined until after the 72-hour post-last dose blood draw and will come back for the final 96-hour post-last dose blood draw the following day at the Study Exit visit.
- Vital signs (blood pressure, heart rate, and respiratory rate): pre-last dose and approximately 1, 2, 4, 6, 8, and 12 hours post-last dose, and once a day until end of confinement.
- 12-lead ECG: pre-last dose and approximately 1, 2, 4, 6, 8, and 12 hours post-last dose and once a day until end of confinement.
- PK blood samples: a total of 12 blood samples will be collected for the last dose: at pre-last dose and 1.5, 3, 5, 7, 9, 12, 24, 36, 48, 72, and 96 hours post-last dose.
- Oxygen saturation via pulse oximetry will be measured: pre-last dose and at 1.5, 4.5, and 8 hours following the last dose (if morning dose), and at 2 hours following the last dose (if evening dose). Pulse oximetry measurements may be collected within 10 min before or after the specified time point. Oxygen saturation will be monitored via pulse continuous oximetry beginning at bedtime and continuing overnight until waking time through end of confinement with oxygen saturation measurements specifically recorded at approximately midnight and 4 am.
- WI-NRS will be performed on a daily basis, to be collected twice per day until end of confinement: once within an hour (+/- 1 hour) of completing their morning and evening meals, if applicable. Subjects will fill in the “Nighttime Itch” form in the morning and the “Daytime Itch” form in the evening.

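### The dose-limiting toxicity definition describes a dose with events in 2 subjects while the operating rules need one subject's event, and it names only Grade 3, so related Grade 4-5 events do not count by grade if it is read literally

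*Protocol*

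**What the plan says.** The same definition stands in three places: the protocol Synopsis (Dose Escalation Stopping Rules), protocol section 9.14 and SAP section 3.6. A DLT is "defined as the dose at which a confirmed Grade 3 adverse event develops in any 2 subjects", with the added conditions that the event is related to the product and unlikely to be due to the disease. The same paragraph adds a second criterion: a sustained overnight oximetry drop counts as a DLT TEAE (treatment-emergent adverse event). That criterion is not tied to a grade.

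The rules then use the term for one subject's event. Section 9.11.1 says that "any subject who experiences a DLT TEAE will not receive further dose of study drug, and safety follow-up procedures" will follow, and section 9.14 has the same individual stop. Sections 9.14.1 and 9.14.4 confirm a dose as a DLT when 2 subjects each develop one there. They close the higher dose when 2 subjects develop DLTs at two different doses. Section 9.11 lists one subject's DLT and a DLT dose confirmed in 2 subjects as separate situations.

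Section 9.15.4.1 requires grading when the event occurs so that DLTs can be monitored. Its Table 4 defines Grades 4 and 5 separately from Grade 3. Neither document says 'Grade 3 or higher' in connection with a DLT.

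**The concern.** These are the plan's mandatory toxicity stops, and a site cannot follow the definition and the operating rules at once. Two questions are left to inference.

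- **Who stops.** If a DLT is a dose with events in 2 subjects, one subject with a related Grade 3 event has not had a DLT. The only single-subject event that the text expressly calls a DLT TEAE is the oximetry drop, so a site could take the individual stop to cover oximetry alone. Section 9 has two sites running the study jointly, and they could differ.
- **Which grades count.** With Grade 3 named alone, a more severe related event carries no weight by grade in either the individual stop or the 2-subject rule.

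In Part 2 the classification also decides which follow-up a stopped subject gets, because section 9.11.2 reserves Early Termination for reasons unrelated to DLT.

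**Working it through.** The plan states no operating characteristic for the stopping rules, so there is no figure to reproduce. The check has three steps.

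**1. Definition against the rules that use it**

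| Rule | What it needs | Under the definition |
|---|---|---|
| Individual stop (9.14, 9.11.1) | One subject's event | Fails, except for oximetry |
| Same-dose rule (9.14.1, 9.14.4) | Two subjects, each with a DLT | Circular: the count of 2 is already in the definition |
| Two-different-doses rule (9.14.1, 9.14.4) | One subject's DLT at each of two doses | Fails: one event per dose makes neither dose a DLT |
| Severe group (9.14.3) | Two severe subjects, each with a DLT | Circular, as above |
| Part 2 exit (9.11) | One subject's DLT distinct from a confirmed DLT dose | The distinction disappears |

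All five rules work if a DLT is one subject's event and a DLT dose is a dose with 2 of them. That is the better reading.

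**2. Literal count by grade**

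The rule needs 2 qualifying subjects at one dose. Two related Grade 3 events count as 2 of 2. One Grade 3 and one Grade 4 count as 1 of 2. Two Grade 4 events count as 0 of 2. The exception is an event that also meets the overnight oximetry criterion.

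**3. Upper limit on further dosing in Part 2**

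The section 9.4 titration table has 24 doses, 6 at each of 27, 54, 108 and 162 mg. After an event at the first dose of a level, 6 − 1 = 5 doses remain at that level. For the three higher levels they are 12 hours apart, so the last falls 5 × 12 = 60 hours later.

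| Level | Same-level doses left | Higher-level doses left | Same-level share |
|---|---|---|---|
| 54 mg | 5 × 54 = 270 mg | 12 | 5/17 = 29% |
| 108 mg | 5 × 108 = 540 mg | 6 | 5/11 = 45% |
| 162 mg | 5 × 162 = 810 mg | 0 | 5/5 = 100% |

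The split matters because of the tolerability condition in section 9.4: "Subjects will remain at each dose level for 2-3 days (minimum 5 consecutive doses) with dose escalation predicated on tolerability of the prior dose". It governs moves to a higher level, not repeat doses at the same level, and it refers to section 9.14.4, the DLT rules, for its criteria. The counts are ceilings that assume no Investigator or Committee action. In Part 1 each level is a single dose, so no same-level doses remain.

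**Follow-up in Part 2.** The DLT Follow-Up Period (9.11.1) has ECGs at 1, 2, 4, 6, 8 and 12 hours after the last dose and then daily, confinement to 72 hours and PK samples to 96 hours, where feasible. Early Termination (9.11.2) has an ECG before discharge, and PK samples at the same nominal times but only until discharge.

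**The case against.** The strongest reply is that no site would be misled. Section 9.11 separates the two senses, the operating rules all point to the subject-level meaning, and most readers will take Grade 3 as a floor. On the two senses this largely stands: the intent can be inferred. On grade it is weaker, because no text supplies the floor.

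A reader might go further and infer that a subject with a life-threatening related event would go on being dosed. The documents do not support that:

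- Combined data are "evaluated by a Safety Committee at the completion of each cohort dose level before proceeding to the next cohort dose level". The review is compulsory, although its outcome is a judgement.
- Under section 9.1 the Investigator must "review and confirm that subjects continue to meet all inclusion and exclusion criteria prior to advancing subjects to the next cohort". Section 8.3 excludes anyone with this history: "Subject has a history of anaphylaxis, a documented hypersensitivity reaction, or a clinically significant reaction to any drug". A related severe reaction would ordinarily meet that, so repeated entry to later Part 1 cohorts is close to unreachable.
- The Investigator can stop escalation for any worrying event (9.14), subjects can be withdrawn for safety (9.13), serious events are reported within 24 hours (9.15.5), and the study can be terminated (section 10).

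Nor can it be said that no mandatory stop reaches Grade 4-5 events. The oximetry criterion does so regardless of grade, and respiratory depression is the boxed warning on the parenteral label (5.2.4). It is an overnight criterion, so a daytime event falls outside it.

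A reader might also want a dose closed under the two-different-doses rule withheld from Cohort 5. Section 9.14.2 bars only confirmed DLT doses there, and the Synopsis leaves the dose to be set "as determined by the Safety Committee review of the mild and moderate impaired data". Extending the bar would be a new restriction that could lower the control dose.

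Finally, drug-related serious events occurred in 8 of 718 exposed subjects (8/718 = 1.1%; 5.1.1.1). This is context only: seriousness is not grade, and the figure is not for hepatic impairment. The documents give no Grade 3-5 rate, so no probability is claimed here.

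**Conclusion.** The definition is wrong as written in all three places. It describes a dose with events in 2 subjects where the rules need one subject's event. It leaves related Grade 4-5 events uncounted by grade, with overnight oximetry as the only criterion that applies whatever the grade.

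This should be fixed, but it is not a fatal flaw. The subject-level intent can be recovered from the operating rules, and the other controls make continued dosing after such an event unlikely. They do not replace a stated grade threshold, and they do not settle which Part 2 follow-up applies. The ceiling of 5 same-level doses holds only if Part 2 is run, which the plan leaves open, and only if nobody acts.

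The effect is on subject safety and consistency between sites. No SAP analysis uses DLT or the maximum safe dose, so the PK comparison of impaired and healthy subjects is untouched.

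**What to change.** Separate the two terms:

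- *Subject-level DLT:* one confirmed adverse event of Grade 3 or higher that is related to the product and unlikely to be due to the disease process, or the overnight oximetry event as now described.
- *Confirmed DLT dose:* a dose at which at least 2 subjects have a subject-level DLT.

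Align the Synopsis, protocol sections 9.11.1 and 9.14 to 9.14.4, and SAP section 3.6. Leave the Cohort 5 rule in 9.14.2 as it is in substance.

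The change adds no procedures. It needs a protocol amendment with ethics committee approval before use (section 14.1) and matching SAP text. A few subjects may stop earlier, with incomplete PK profiles. It adds no cohort-level pause after a single Grade 4-5 event; that decision stays with the Investigator and the Safety Committee.
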